Aim 3: Quantify LARC continuation over a 6-18 month follow-up period among LARC initiators within the SBHC network following implementation of telehealth-supported LARC provision. Using EHR data for all patients who initiated LARC, we will use Kaplan-Meier survival curves to assess LARC discontinuation overall, and Cox proportional hazard models to compare LARC continuation by LARC type.

Aim 3.1 (Primary Efficacy Outcome): 12-month continuation of LARC using telehealth-supported care among SBHC patients compared to LARC continuation rates among adolescents age 25 years and under as documented in a recent meta-analysis. Continuation rates will be expressed both as rates at 6 months and 12 months post-initiation, and using Kaplan-Meier curves to model discontinuation. Continuation rates in this setting will be compared to rates from a recent meta-analysis among adolescents and young adults that found 12-month continuation rates of 85.3% (primary efficacy outcome) for contraceptive implants and IUDs in the US-based studies (Usinger, Gola, Weis & Smaldone, 2016).

Aim 3.2 (Exploratory, pending feasibility) Continuation compared to pre-Telehealth. Compare 12-month continuation rate following introduction of telehealth to 12-month continuation among LARC initiators seen during the 18 month period prior to introduction of telehealth (June 2018-December 2019) *pending ability to export data from the prior electronic health record.*

Hypothesis:

We hypothesize that, in this sample of adolescents receiving telehealth-supported LARC services in a network of SBHCs, the LARC continuation rate at 12 months will be non-inferior to the 12-month continuation rate among adolescents and young adults age <25 (85.3%) as documented in a meta-analysis

comparing contraceptive implants and IUDs, in the absence of telehealth. The non-inferiority margin is chosen to be 10 percentage points less than that of the current standard of care (SOC) in US as such difference represents the maximum tolerable margin for inferiority while clinically important impact of proposed intervention can still be preserved.

Background/ Rationale

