Thematic analysis will be used to describe the qualitative data generated from the interviews. Using an inductive approach, two coders will scan a random selection of transcripts to generate initial codes; working from these, we will generate a code-book that lists major themes, specifies categories

emerging from the data, and descriptions of each theme. The first 10 transcribed interviews will be jointly coded using Dedoose; then, inter-rater coding agreement will be assessed. The entire study team will: resolve discrepancies in coding, clarify theme definitions, and collapse or expand themes as needed.

Primary efficacy outcome (Aim 3): Continuation post-LARC initiation

The primary outcome for this study (3.1) will be absolute continuation rate 12 months post-initiation (dichotomous yes/no continuation), with analyses also examining continuation at 6 months (yes/no).

Aim 3.1 (Primary Efficacy Outcome): Overall 12-month continuation of LARC using telehealth-supported care compared to LARC continuation rates among adolescents age 25 and under as documented in a meta-analysis of US studies.

The primary outcome will be the proportion of patients continuing their initiated LARC method at 12 months post-initiation. Hypothesis: We hypothesize that, with the non-inferiority margin of 10 percentage point difference, in this sample of adolescents receiving telehealth-supported LARC services in a network of SBHCs, the LARC continuation rate at 12 months will be non-inferior to the reported 12-month continuation rate among adolescents and young adults age under 25 years (85.3%) in the US who initiated contraceptive implants or IUDs the absence of telehealth (Usinger, Gola, Weist & Smaldone, 2016).

Statistical Methods (Aim 3.1):

Continuation rates will be expressed as rates at both 6 months and 12 months post initiation, and time to discontinuation will be visualized using Kaplan-Meier curves.

We will test the primary null hypothesis $H_0: p \leq 0.753$ (i.e., 10 percentage points less than the reference rate of 0.853) using one-sample, one-tailed Z-test, where p is the LARC continuation rate at 12 months for participants who receive telehealth-supported LARC services in a network of SBHCs, and the reference the proportion (of 0.853) was chosen from the finding of the meta-analysis mentioned above.

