Additionally, we will use Chi-squared tests to compare continuation (yes, continued/no, discontinued) between LARC types (contraceptive implant vs. IUD) at two time points: 6 months and 12 months post-initiation. Adjusted analyses using logistic regression will be conducted to compare the continuation at 6 and 12 months (yes or no) separately between contraceptive implant and IUD patients, adjusting for covariates (age, race/ethnicity, gender identity, sexual orientation, sexual activity in last 90 days, gravidity, parity). Operationalization of these covariates is outlined in Aim 1.

Power/Sample Size (Aim 3.1):

The study anticipates enrolling 113 patients, with 102 patients included in the continuation analyses for Aim 3 (primary outcome). Our sample size estimates are based on conservative SBHC clinical data from 2018-2019 and from the first seven months of 2019-20 (which was disrupted by both the transition to a new EHR Epic system and school and SBHC closures due to COVID-19); during the July 2018 to January 2020 time period, there were, respectively, 129 LARC initiations (86 contraceptive implant, 43 IUD), and 44 LARC initiations (41 implant, 3 IUD). These sample size estimates are conservative, as the SBHCs have three newly-hired and trained medical providers since the 2019-20 disrupted year.

We anticipate having complete data for the continuation analyses sample size ($n=102$). Using the new Epic EHR, at each visit within the NYP clinical network – the participating study sites in the SBHCs, as well as the emergency department, inpatient and outpatient clinics – the health care provider is required to conduct reconciliation of medications and document it in the Epic EHR. The medical providers ask every patient at every visit what their current contraceptive method is – confirming the presence of the method, and documenting in two places in the EHR (in the contraception and in medications sections). These analyses will be able to assess continuation (presence of the device at a visit) and censoring

(device removal, device removal with re-insertion).

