With a sample size of 102 and the margin of non-inferiority of 10 percentage points, the proposed study has 80% power to declare the non-inferiority of the telehealth-supported LARC services in a network of SBHCs in a one sample, one-sided Z test. This power analysis is for the primary efficacy outcome of interest, i.e., LARC continuation rate at 12 months. The reference LARC continuation rate at 12 months of 0.853 was obtained from the meta analysis conducted by Usinger, Gola, Weis & Smaldone in 2016. The studies included in their meta-analysis collected sample in the US with participants in those studies being young women aged 25 years and younger using a range of contraceptive methods. Therefore, if the true LARC continuation rate at 12 months is 0.753 or higher, the study is adequately powered to establish the non-inferiority of telehealth-supported approach. In the CHOICE Project, 12-month continuation of Copper IUDs among participants age 14-19 was 75.6% (Rosenstock et al., 2012).

Aim 3.2 (Exploratory, pending feasibility) Continuation compared to pre-Telehealth. Pending examination of the feasibility of constructing a pre-telehealth research database using the prior EHR system, compared to continuation rates within the same network prior to the implementation of telehealth-supported care, we will compare 12-month continuation (yes/no) following introduction of telehealth to 12-month continuation among LARC initiators seen the 18 month period prior to introduction of telehealth (June 2018-December 2019) *pending ability to export data from the prior electronic health record.*

3. Study Procedures

AIM 1

Participant enrollment – Aim 1: All patients who receive care at the SBHC provide informed consent for care, as well as record review for quality assurance purposes. Analyses for Aim 1 will include all female patients who have a “reproductive health visit,” which includes contraceptive counseling, contraceptive management, or contraceptive method initiation, during the study period. All patients who have a telehealth consultation with a SBHC medical provider for LARC services (conservatively estimated n=113) will be considered enrolled patients once the data are extracted from the EHR, and these will inform uptake analyses for Aim 1.

AIM 2

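### The primary test supports a claim about a fixed 75.3% goal, not about the true standard-of-care rate, because the 85.3% reference enters without its uncertainty

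*Combined protocol and SAP*

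**What the plan says.** The points below come from sections 1 and 2 of the combined protocol and SAP.

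- **Margin (section 1, Hypothesis).** "The non-inferiority margin is chosen to be 10 percentage points less than that of the current standard of care (SOC) in US". This refers to a population rate under current care.
- **Test (section 2, Statistical Methods, Aim 3.1).** H0: p ≤ 0.753, "i.e., 10 percentage points less than the reference rate of 0.853) using one-sample, one-tailed Z-test". On the source of the benchmark: "the reference the proportion (of 0.853) was chosen from the finding of the meta-analysis mentioned above".
- **Operative hypothesis (section 2, Aim 3.1).** It compares the cohort with the reported rate of 85.3%.
- **Power (section 2, Power/Sample Size, Aim 3.1).** "With a sample size of 102 and the margin of non-inferiority of 10 percentage points, the proposed study has 80% power". What that power is for, in the plan's terms, is a finding that the telehealth service itself is non-inferior. On the benchmark again: "The reference LARC continuation rate at 12 months of 0.853 was obtained from the meta analysis". On missing data: "We anticipate having complete data for the continuation analyses sample size", with n=102.

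The documents give no confidence interval, standard error, number of studies or heterogeneity for the 85.3%. They state no alpha for this test and plan no sensitivity analysis over the reference. There is no concurrent control. Aim 3.2, the comparison with the same network before telehealth, would estimate a reference from data, but it is exploratory and depends on whether old records can be exported.

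**The concern.** A pooled estimate has sampling error, and rates also differ between studies and settings. The planned Z-statistic contains only the variance of this cohort. If the result is read as a comparison with what standard care really achieves, part of the uncertainty is missing. The study could pass because the published figure happened to be low, or fail because it happened to be high, and neither possibility is in the stated power.

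The documents themselves hint that rates vary. Power/Sample Size (Aim 3.1) cites 75.6% for copper IUDs at ages 14-19 in another project, which is 85.3 − 75.6 = 9.7 points below the reference and nearly the whole margin. That is one method in one age band, so it does not estimate the reference's standard error.

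At stake is the wording of the primary conclusion: whether the study may say only that continuation exceeds 75.3%, or may also say that telehealth-supported care is non-inferior to standard care.

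**Working it through.** **Inputs from the documents:** p0 = 0.753, p1 = 0.853, n = 102 complete, one-sided one-sample Z-test, stated power 80%.

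**Assumed:** one-sided alpha 0.05 (z = 1.645), and a reference standard error s of 0.01, 0.02 or 0.03. No value of s can be taken from the documents.

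**1. Reproduce the plan's power, reference fixed.**

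SE0 = √(0.753 × 0.247 / 102) = 0.0427

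SE1 = √(0.853 × 0.147 / 102) = 0.0351

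Power = Φ[(0.10 − 1.645 × 0.0427) / 0.0351] = Φ(0.849) = 80.2%. The n for 80% power is 101.5, hence 102.

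The match shows three things.
- The 80% contains no uncertainty in the reference.
- It is power at a true rate of 0.853. The same section says "if the true LARC continuation rate at 12 months is 0.753 or higher, the study is adequately powered", but power at exactly 0.753 equals alpha.
- Alpha 0.05 is an inference. At 0.025 the same formula gives 67.9%. At 0.025 with the variance under the alternative throughout, power is 81.4% and the required n is 99, which is close but is not 102.

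**2. Error of the planned test against the true standard-of-care rate.** Let θ be that rate and let telehealth sit exactly at θ − 0.10. The planned test rejects when the observed rate exceeds the published reference − 0.10 + 1.645 × SE0. The difference between the two estimates has variance SE0² + s², so the error averaged over the sampling of both is

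P(Z > 1.645 × SE0 / √(SE0² + s²)).

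**3. Power at equality of a test that carries s.**

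P(Z > (1.645 × √(SE0² + s²) − 0.10) / √(SE1² + s²)).

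**4. Observed rate that such a test needs:** 0.753 + 1.645 × √(SE0² + s²).

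| Assumed s | Averaged error, planned test | Power, test carrying s | Observed rate needed | Patients of 102 |
|---|---|---|---|---|
| 0 (as planned) | 5.0% | 80.2% | 82.3% | 84 |
| 0.01 | 5.5% | 77.8% | 82.5% | 85 |
| 0.02 | 6.8% | 71.1% | 83.1% | 85 |
| 0.03 | 8.9% | 62.1% | 83.9% | 86 |

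The last column rounds 102 × the unrounded rate up to a whole patient (83.97, 84.16, 84.72 and 85.56). Over this range the stricter test changes the decision only if 84 or 85 patients continue.

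At one-sided 0.025 the averaged error for the three values of s is 2.8%, 3.8% and 5.4%, and the power is 65.0%, 57.5% and 48.0%.

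**5. Error for a given true standard-of-care rate.** The planned cut-off stays at 0.8232.
- True rate 0.873, telehealth at 0.773: z = (0.8232 − 0.773) / √(0.773 × 0.227 / 102) = 1.21, error 11.3%.
- True rate 0.833, telehealth at 0.733: z = (0.8232 − 0.733) / √(0.733 × 0.267 / 102) = 2.06, error 2.0%. Power at equality is then 60%.

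The error can therefore fall on either side of 5%.

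**The case against.** The strongest reply is that the plan tests what it says it tests. The operative hypothesis names the reported rate, and H0 is a fixed number. A fixed performance goal is a legitimate design, and against it the Z-test keeps approximately its nominal level and the 80% is right. This stands. A reader might infer that the primary test is invalid or that its power is miscalculated, and the documents do not support either. The gap opens only when success is read as non-inferiority to the true standard-of-care rate. The margin rationale and the power statement do invite that reading.

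A reader might also infer that the study's error is simply above nominal. That holds only on average over hypothetical repetitions of the meta-analysis. The published value is already fixed, and given that value the error may be higher or lower (step 5).

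Size is a fair objection too. The range of 1 to 3 points has no source in the documents. At 1 point or less the effect is small: error at most 5.5% and a power loss of about 2.4 points. Only the published interval can settle this.

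Finally, all the power figures assume 102 patients complete at 12 months. Section 3 (Aim 3) gives the last enrollees 6 months of follow-up. If enrolment were uniform and about half reached 12 months (n about 51), power with a fixed reference would be about 50%, and a 1-point standard error would change it by about 1 point. That is a separate matter, but it means the 78%, 71% and 62% should not be taken as forecasts.

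**Conclusion.** The point holds as a limit on interpretation. The primary test compares the cohort with a fixed goal of 75.3%. Its error level and its 80% power belong to that comparison and do not extend to the standard-of-care rate. How far they fall short depends on a standard error that the documents do not give: slight at 1 point and substantial at 3 points, on an inferred one-sided alpha of 0.05 and complete data on 102 patients.

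A reader might infer that once the standard error is added and the test still rejects, non-inferiority to standard of care is established. The documents do not support that. The standard error of a pooled mean leaves out the between-study spread that matters when the figure is carried to a new setting, and no such adjustment makes an uncontrolled cohort comparable with the reference. The title of the cited review in the References concerns intrauterine contraception, whereas 86 + 41 = 127 of the 129 + 44 = 173 historical initiations in Power/Sample Size (Aim 3.1) were implants.

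This is a cheap improvement. It does not call for replacing the primary test.

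**What to change.** 1. Keep H0: p ≤ 0.753 and state its one-sided alpha.
2. Word the primary conclusion as 12-month continuation exceeding the fixed goal of 75.3%.
3. In Power/Sample Size (Aim 3.1), label the 80% as conditional on a fixed reference, a true rate of 0.853 and 102 complete patients. Correct the sentence that calls the study adequately powered from 0.753 upward.
4. Report the published confidence interval of the 85.3%. Pre-specify one sensitivity analysis that repeats the test with the reference's uncertainty in the variance, using that interval and, if available, the prediction interval or between-study variance. Report whether the conclusion holds, and give the power under that analysis.
5. Do not make passing the sensitivity analysis a condition that permits an unqualified claim of non-inferiority to standard of care.

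The cost is a few sentences and one calculation, with no added patients or data. The price is a more modest claim and a less favourable power figure under the sensitivity analysis.

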This two-year study will have three phases: 1) a 4-month study initiation phase; 2) a 12-month enrollment and surveying phase; 3) and a 6-month follow-up observation phase. Continuation analyses will rely on person-time, so that study participants will contribute a minimum of 6 to a maximum of 19 months observation time, depending on their time of enrollment.

Statistical Procedures. [name] will have lead responsibility for conducting statistical analyses, supervising data cleaning, and logic checks conducted by the Research Coordinator, and working with the Biostatistician on model building. As this is a prospective observational study that seeks to enroll all patients who receive telehealth-supported LARC services over a 12-month period, the sample size will be determined by patient flow and participation rates.

Aim 1 (Secondary Outcome): Quantify uptake of LARC (contraceptive implant, IUD) within the SBHC network following implementation of telehealth-supported LARC provision

Aim 1.1 Making use of a newly-implemented electronic health record (EHR) system, Epic, we will assess uptake of contraception, quantifying the number and proportion of contraceptive method initiation (uptake), assessing each month:

- 1) absolute number of contraceptive counseling visits via telehealth;
- 2) absolute number of LARC telehealth consultations (a LARC consultation being defined as a visit in which an insertion is scheduled);
- 3) absolute number of LARC initiations by type (contraceptive implant, IUD);
- 4) LARC initiation visits as a proportion of contraceptive counseling visits (overall, and by LARC type [contraceptive implant, IUD]);

¹ The current SBHA Census does not provide data on how many SBHCs dispense contraception; the most recent data on this are from the 2007-08 census and are not presented here.

- 5) LARC initiation visits as a proportion of all contraceptive method initiation visits (overall, and by LARC type);
- 6) LARC initiation visits as a proportion of LARC telehealth consultations (defined as a visit in which a LARC initiation was scheduled; overall and by LARC type);

and 7) relative share of initiations of contraceptive implant and IUD, among LARC initiators.

Statistical Methods (Aim 1.1)

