Follow-up observation (Continuation Analyses, Aim 3): Follow-up observation will continue for 6 months after the enrollment phase has completed; therefore, participants enrolled in the first month will have 18 total months observation, while those enrolled in the last month will have 6 months. In 2018-19, in the network of 6 SBHCs, 2,425 unique female patients had a total of 12,398 visits (for any purpose), representing an average of 5 SBHC visits per female patient in the academic year.² At each visit to the SBHC, regardless of visit type, all female patients have their medications, including contraceptive method, reconciled and confirmed in the medical record. With the new Epic EHR system, export of all LARC-related procedure codes (insertions, removals, removal with replacement) and device codes (e.g. Nexplanon, Liletta, Paragard) *in addition to all visits* (with corresponding data on current contraceptive method) will enable us to identify person-time events including censoring. At all New York Presbyterian (NYP) sites, the health care provider is required to conduct reconciliation of medications and document it in the EHR at every visit. The SBHC medical providers ask every SBHC patient at every visit what their current contraceptive method is – confirming the presence of the method, and documenting this in two places in the EHR (in the contraception history section, and in the medications section).

Compensation.

All Aim 2 survey and interview participants will receive compensation for their time and effort in the form of an Amazon electronic gift card, purchased through the Mailman School of Public Health. Compensation is as follows:

Quantitative survey participants will receive, as compensation for their time and effort, an Amazon gift card valued at \$10 at the conclusion of the survey. The card will be sent to participants electronically.

Qualitative interview participants will receive, as compensation for their time and effort, an Amazon gift card valued at \$25. The card will be sent to participants electronically.

4. Study Subjects

Subject Population Justification:

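### The implant-versus-IUD continuation comparison is a Cox model in the aims but only fixed-time Chi-square and logistic tests in the methods, with no lead analysis named

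*Combined protocol and SAP*

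**What the plan says.** Section 1, Specific Aims, Aim 3 plans "Cox proportional hazard models to compare LARC continuation by LARC type", using EHR data on all initiators. Section 2, Study Design and Statistical Procedures, adds: "Continuation analyses will rely on person-time".

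Statistical Methods (Aim 3.1) takes a different route. Kaplan-Meier curves serve only to visualise time to discontinuation, and Cox is not mentioned. For implant versus IUD the text reads: "Additionally, we will use Chi-squared tests to compare continuation (yes, continued/no, discontinued) between LARC types (contraceptive implant vs. IUD) at two time points", namely 6 and 12 months. It continues: "Adjusted analyses using logistic regression will be conducted to compare the continuation at 6 and 12 months (yes or no) separately", "adjusting for covariates (age, race/ethnicity, gender identity, sexual orientation, sexual activity in last 90 days, gravidity, parity").

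Follow-up is staggered. Section 3, Aim 3, says "participants enrolled in the first month will have 18 total months observation, while those enrolled in the last month will have 6 months"; section 2 gives a maximum of 19 months. Power/Sample Size (Aim 3.1) expects complete data, "with 102 patients included in the continuation analyses for Aim 3 (primary outcome"), and its closing sentence places device removal, with or without re-insertion, under censoring.

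No section ranks these analyses, states an alpha, or gives a hypothesis or power for the LARC-type comparison.

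**The concern.** One clinical question, whether implant and IUD users differ in continuation, is given up to five p-values: one from Cox, two from Chi-square tests and two from logistic models. They estimate different quantities (a hazard ratio, and differences or odds ratios at two times). Without a named lead, the analysis that decides the conclusion can be chosen after the results are seen.

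The choice also affects precision. An analyst who follows the detailed methods would run only the fixed-time tests. At 12 months these cannot use patients observed for less than 12 months, nor removals after month 12, although the design collects both. The Cox model, which would use them, has no stated event, censoring rule or covariates. As Power/Sample Size (Aim 3.1) is worded, a removal could be coded as a censoring, when in a model of discontinuation it is the event.

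**Working it through.** **1. The plan's own figure.** The only stated power is 80%, for the primary Z-test. With n = 102, p0 = 0.753, p1 = 0.853 and an assumed one-sided alpha of 0.05:

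Power = Φ[(0.100 − 1.645 × √(0.753 × 0.247/102)) / √(0.853 × 0.147/102)] = Φ[(0.100 − 0.0702)/0.0351] = Φ(0.849) ≈ 80.2%.

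It reproduces. It says nothing about implant versus IUD.

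**2. Inputs for the LARC-type comparison.**
- From the documents: n = 102; follow-up 6 to 18 months; 12-month continuation 0.853. The device mix comes from "129 LARC initiations (86 contraceptive implant, 43 IUD), and 44 LARC initiations (41 implant, 3 IUD"): 127 implants and 46 IUDs, so 46/173 = 27% IUD, or 43/129 = 33% in the first period.
- Assumed: entry uniform over 12 months, constant hazards, two-sided 0.05 per test, and all hazard ratios. Cox is represented by its score (log-rank) test.

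**3. Information used by each analysis (no difference by type).** λ = −ln(0.853)/12 = 0.01325 per month.
- 12-month tests: half the cohort has 12 months of observation, so about 51 patients and 51 × 0.147 = 7.5 removals.
- 6-month tests: all 102 patients, 102 × (1 − √0.853) = 7.8 removals.
- Time-to-event: 102 × [1 − (e^(−6λ) − e^(−18λ))/(12λ)] = 14.9 removals.

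**4. False positives.** Two independent tests would give 1 − 0.95² = 9.75%, and five would give 1 − 0.95⁵ = 22.6%. The planned tests share data, so their correlation has to be simulated (27% IUD, staggered follow-up, 5,000 trials):
- log-rank alone: 4.3%
- the two Chi-square tests: 7.6%
- both Chi-square tests plus log-rank: 9.7%
- all five: 10.9% (11.5% with 33% IUD; 10.8% with complete follow-up)

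**5. Power (27% IUD, implant continuation 0.853 at 12 months, 2,000 trials per row).**

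| Follow-up | Hazard ratio, IUD vs implant | Log-rank/Cox | Chi-square 6 mo | Chi-square 12 mo | Logistic 6 mo | Logistic 12 mo |
|---|---|---|---|---|---|---|
| 6-18 months | 2 | 33% | 22% | 21% | 18% | 16% |
| 6-18 months | 2.5 | 54% | 35% | 31% | 31% | 27% |
| 6-18 months | 3 | 71% | 48% | 44% | 43% | 39% |
| Complete | 2.5 | 68% | 34% | 52% | 31% | 51% |

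A second scenario assumes 12-month discontinuation of 10% (implant) and 30% (IUD), a hazard ratio of ln 0.7/ln 0.9 = 3.4. Power is about 70% for log-rank, 44-46% for the 6-month Chi-square and 43-46% for the 12-month Chi-square. In that scenario, when at least one of these three tests is significant, they do not all agree about 64% of the time.

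**6. Covariates.** With the Aim 1.2 categories, age, race/ethnicity, gender identity and sexual orientation take 3 degrees of freedom each, and three binary covariates take 1 each: 4 × 3 + 3 = 15. Against about 15 removals that is roughly one event per parameter. With assumed category frequencies and no true difference, a Cox model with the full list rejects 9.3% of the time by likelihood-ratio test (5.4% by Wald; 1,000 trials). If the two logistic models carry the full list and use likelihood-ratio tests, the chance that any of the five tests is falsely positive rises to 26% with staggered follow-up and 19% with complete follow-up.

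**The case against.** The strongest reply is that this is a secondary contrast in an observational study. It has no hypothesis or power statement and is introduced as an addition to the one primary test. That stands, and it limits the weight of the point.

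Second, the methods can be complementary. The declared outcome is yes/no at 12 months, with 6 months also examined, so binary tests match it, and reporting unadjusted beside adjusted results is routine. This also stands: the analyses need not be removed, only ranked.

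Third, most of the inflation comes from testing at two time points, not from the Cox discrepancy. The Chi-square tests alone give 7.6%; adding the time-to-event test brings it to 9.7%. This is correct.

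Fourth, the plan expects complete data on all 102. That does not remove the point: the stated observation window leaves about half the cohort short of 12 months, and with complete follow-up the time-to-event test still leads, 68% versus 52% at hazard ratio 2.5.

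Fifth, the power ranking depends on proportional hazards and on effect sizes that the documents do not give. At hazard ratio 2 neither approach is adequate, and the Background says that side effects improve between 6 and 12 months, so constant hazards may not hold. This is a fair caution, which the fix takes up.

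A reader might infer that Cox has been dropped, so that the LARC-type result rests wholly on the weaker methods. The documents do not support that: Cox remains in Aim 3 and is missing only from the detailed methods.

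**Conclusion.** The aims and the methods disagree on how implant and IUD continuation will be compared, and nothing says which analysis decides. At an assumed two-sided 0.05 per test, the chance of at least one false positive is about 10%, roughly double that of one named test. The fixed-time tests are also clearly less powerful under constant hazards: 16-22% against about 33% at hazard ratio 2, and 43-46% against about 70% at about 3.4. Alpha, hazard ratios, constant hazards and uniform entry are assumptions.

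Two stronger readings should be resisted. The false-positive rate is not 22.6%, because the five tests are strongly correlated. Nor does the point touch the primary non-inferiority conclusion, which rests on a separate one-sample test. This is a worthwhile correction to a secondary analysis.

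**What to change.** In Statistical Methods (Aim 3.1):

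- Name one lead analysis for LARC type, at a stated alpha: an unadjusted Cox or log-rank comparison, or a Cox model with at most one or two pre-specified covariates. Do not carry over the seven-covariate list.
- Define the event as device discontinuation and censor at end of observation. Reconcile this with the sentence in Power/Sample Size (Aim 3.1) that lists removal, and removal with re-insertion, under censoring.
- Report Kaplan-Meier continuation by type at 6 and 12 months, with the difference and 95% confidence interval.
- Label the Chi-square and logistic comparisons as supportive.
- Pre-specify a check of proportional hazards.

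The cost is wording only, with no new data or patients. The downside is that a hazard ratio is less familiar to clinicians than a month-12 percentage and relies on proportional hazards; the Kaplan-Meier percentages and the check address both.
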